The purpose of this study is to assess the safety and efficacy of the Resolute Onyx Zotarolimus-Eluting Coronary Stent System for the treatment of *de novo* lesions in native coronary arteries that allows the use of a 2.0 mm diameter stent.

3. Study Design

This study is designed as a single-arm, open-label multi-center study.

3.1. Treatment(s) and Subject Enrollment

At least 100 subjects with ischemic heart disease due to *de novo* stenotic lesions within native coronary arteries that meet the eligibility criteria and sign the informed consent form will be asked to participate in this trial. All subjects who consent will be asked to participate in the 13 month angiographic subset until at least 20 subjects have been enrolled in this subset. Subjects may receive treatment in up to two lesions, if the lesions are located in separate target vessels. Only one lesion may be treated in a single target vessel. Core size lesions should be treated with the currently approved Resolute Integrity stent. All treatment with the study stents is to be performed during a single index procedure.

In the event of one lesion to be treated with a 2.0 mm study stent and another lesion to be treated with a core size (2.25 mm - 4.0 mm) Resolute Integrity stent, the subject should be treated first with the core-sized stent. If the treatment of the first lesion fails or if the subject becomes unstable before a 2.0 mm study stent is attempted (stent introduced into guide catheter), the subject will not be enrolled, will not be followed, and will not be included in the primary analysis of this trial. Another subject should be enrolled to replace this subject for the primary analysis. If the treatment with the 2.0 mm study stent is attempted (stent introduced into guide catheter) but not implanted, the subject will be considered part of the Intention-to-Treat population (ITT) and will be followed through the 12 month endpoint and will be included in the primary analysis of this trial.

For subjects who have more than one lesion planned for treatment, FFR should be performed in the vessel expected to receive the 2.0 mm study stent to demonstrate the functional need for treating such a lesion, unless demonstrated by other means (clinical evidence and/or positive functional study).

The trial will be conducted at a maximum of 25 investigational sites within the United States (US) and Japan. Sites are allowed to enroll a maximum of 20 subjects per site or until study enrollment has been completed, whichever comes first. The expected time of participation in the trial for each subject is three years.

3.1.1. General Inclusion Criteria

Subject must meet **all** of the following criteria to be eligible for treatment in the trial:

1. Subject is ≥ 18 years old or ≥ 20 years old if in Japan
2. Subject is an acceptable candidate for percutaneous coronary intervention (PCI), stenting, and emergent coronary artery bypass graft (CABG) surgery
3. Subject has clinical evidence of ischemic heart disease. For single vessel disease: stable or unstable angina alone is sufficient. For multi-vessel treatment: a positive functional study or FFR to demonstrate functional need in 2.0 mm small vessel.
4. Female subjects of childbearing potential must have a negative pregnancy test within 7 days before the trial procedure
5. Subject or subject's legal representative has been informed of the nature of the trial and agrees to its provisions and has provided written informed consent as approved by the Institutional Review Board (IRB) of the respective investigational site
6. Subject agrees to comply with specified follow-up evaluations and to return to the same investigational site where the procedure was performed if participating in the angiographic subset.

3.1.2. Angiographic Inclusion Criteria

The subject and each target lesion/vessel must meet **all** of the following angiographic criteria for the patient to be considered for inclusion in the trial:

1. The subject requires treatment of either:
 - a. A single target lesion amenable to treatment with a 2.0 mm stentOR
 - b. Two target lesions located in separate target vessels, with at least one of the target lesions amenable to treatment with a 2.0 mm study stent
2. Target lesion(s) must be de novo lesion(s) in native coronary artery(ies)
3. Target lesion(s) treated with a 2.0 mm stent must be ≤ 27 mm in length
4. Target lesion(s) must have a stenosis of $\geq 50\%$ and $< 100\%$
5. At least one target vessel(s) must have a reference vessel diameter (RVD) ≥ 2.0 mm and < 2.25 mm by visual estimate
6. Target vessel(s) must have a thrombolysis in myocardial infarction (TIMI) flow ≥ 2

Note: Measurements may be made by careful visual estimate, on-line QCA, or IVUS.

3.1.3. General Exclusion Criteria

Subjects will be excluded from the trial if **any** of the following criteria are met:

1. Known hypersensitivity or contraindication to aspirin, heparin and bivalirudin, thienopyridines, cobalt, nickel, platinum, iridium, chromium, molybdenum, polymer coatings (e.g. BioLinx) or a sensitivity to contrast media, which cannot be adequately pre-medicated
2. History of an allergic reaction or significant sensitivity to drugs such as zotarolimus, rapamycin, tacrolimus, everolimus, or any other analogue or derivative
3. Platelet count $< 100,000$ cells/mm³ or $> 700,000$ cells/mm³, or a white blood cell (WBC) count $< 3,000$ cells/mm³ within 7 days prior to index procedure
4. Serum creatinine level > 2.5 mg/dl within 7 days prior to index procedure

5. Evidence of an acute MI within 72 hours of the trial procedure:
 - a) Q wave myocardial infarction (QWMI)
 OR
 - b) Elevated cardiac biomarker values [preferably cardiac troponin (cTn)] with at least one value above the upper reference limit (URL) and with at least one of the following:
 - Symptoms of ischemia
 - New or presumed new significant ST-segment–T wave (ST–T) changes or new left bundle branch block (LBBB)
 - Development of pathological Q waves in the ECG
 - Imaging evidence of new loss of viable myocardium or new regional wall*Note: Subjects with evidence or suspicion of an acute MI (per Investigator or Sub-Investigator determination) must have cardiac enzyme results reviewed prior to enrollment.*
6. Previous percutaneous coronary intervention (PCI) of the target vessel(s) within 9 months prior to the procedure

Note: Refer to Table 1 in Section 3.1.5 for criteria of previous PCI to the target and other (non-target) vessel(s).
7. Planned PCI of any vessel within 30 days post-index procedure and/or planned PCI of the target vessel(s) within 12 months post-procedure. (no staged procedures)

Note: Refer to Table 1 Section 3.1.5 for additional procedure criteria for planned PCI of the target and other (non-target) vessel(s)
8. During the index procedure, the target lesion(s) requires treatment with a device other than percutaneous transluminal coronary angiography (PTCA) prior to stent placement (including, but not limited to, cutting/scoring balloon, atherectomy, laser, thrombectomy, etc.)
9. History of a stroke or transient ischemic attack (TIA) within the prior 6 months
10. Active peptic ulcer or upper gastrointestinal (GI) bleeding within the prior 6 months
11. History of bleeding diathesis or coagulopathy or will refuse blood transfusions
12. Concurrent medical condition with a life expectancy of less than 12 months
13. Any previous treatment of the target vessel(s) for restenosis, including brachytherapy
14. Currently participating in an investigational drug or another device trial that has not completed the primary endpoint or that clinically interferes with the current trial endpoints; or requires coronary angiography, IVUS or other coronary artery imaging procedures

Note: Trials requiring extended follow-up for products that were investigational, but have since become commercially available, are not considered investigational trials.
15. Documented left ventricular ejection fraction (LVEF) < 30% at the most recent evaluation
16. Inability to comply with the required trial antiplatelet regimen (see protocol Section 5.3)

3.1.4. Angiographic Exclusion Criteria

Subjects will be excluded from the trial if **any** of the following criteria are met (for subjects with two target lesions, both target lesions/vessels must not meet any of the criteria below):

1. Target lesion(s) are located in native vessel(s) distal to anastomosis with a bypass graft (including but not limited to saphenous vein graft or a left/right internal mammary artery (LIMA/RIMA)) with more than 40% diameter stenosis anywhere within the graft

Note: A target lesion distal to a graft may be accessed through the graft.
2. Previous stenting in the target vessel(s) :
 - a) within 9 months prior to procedure

- b) ≤ 15 mm from the target lesion(s)
- 3. Target vessel(s) has/have other lesions with greater than 40% diameter stenosis based on visual estimate or on-line QCA
- 4. The target vessel(s) has/have evidence of thrombus
- 5. The target vessel(s) is/are excessively tortuous (two bends $> 90^\circ$ to reach the target lesion)
- 6. The target lesion(s) has/have any of the following characteristics:
 - a) Lesion location is aorto-ostial, or within 5 mm of the origin of the left anterior descending (LAD) or left circumflex (LCX)
 - b) Involves a side branch > 2.0 mm in diameter
 - c) Is at or distal to a $> 45^\circ$ bend in the vessel
 - d) Is severely calcified
- 7. Unprotected left main coronary artery disease (an obstruction greater than 50% in the left main coronary artery)

3.1.5. Criteria for Additional Procedures

Only one target lesion per target vessel for a maximum of two target vessels may be treated during the trial index procedure. Any other lesion in the target vessel(s) can only be treated after 12 months post-procedure. Any lesion in other (non-target) vessels can be treated after 30 days post-procedure with a Resolute Integrity Stent (preferred) or any approved stent. The criteria for pre and planned post-procedure interventions in the target vessel(s) and other (non-target) vessels are provided in Table 1.

Table 1: Previous and Additional Procedure Criteria

Time Point	Target Vessel(s)	Non-target Vessel(s)
Prior to Index		
> 9 months pre-procedure	Any approved treatment, provided: 
 • Target lesion must be at least 15 mm away from a previously placed stent or treatment • No more than 40% stenosis anywhere in the vessel other than the target lesion 	Any approved treatment
9 months to > 30 days pre-procedure	No PCI	Any approved treatment
30 days to > 24 hours prior to index procedure	No PCI	Any bare metal stent provided: 
 • No MACE events resulted if ≤ 30 days from the index procedure • Two post-procedural serial CK-MB measures below the upper limits of normal if ≤ 72 hours

≤ 24 hours prior to index procedure	No PCI	No PCI
Post Index		
≤ 30 days post-procedure	No PCI*	No PCI**
> 30 days to 12 months post-procedure	No PCI**	Resolute Integrity (preferred) or any approved treatment
> 12 months post-procedure	Resolute Integrity (preferred) or any approved treatment for the intended indication	Resolute Integrity (preferred) or any approved treatment for the intended indication

* In case of acute/subacute closure (within 30 days post procedure) the target lesion(s)/segment(s) should be treated with the study device.

** If deemed medically necessary by the Investigator, the subject should receive any necessary treatment

3.2. Endpoints

3.2.1. Primary Endpoint

Target lesion failure (TLF) at 12-months post-procedure, defined as cardiac death, target vessel myocardial infarction (TMVI) (Q wave or non-Q wave) or clinically-driven target lesion revascularization (TLR) by percutaneous or surgical methods.

3.2.2. Key Secondary Endpoints

Secondary endpoints of this trial include the following:

Clinical Endpoints:

- Acute Success (Device, Lesion, Procedure)
- The following secondary endpoints will be assessed at hospital discharge, 30 days, 6 months, and 12 months post-procedure, and annually thereafter through year 3:
 - Cardiac Death
 - Target Vessel Myocardial Infarction (TVMI)
 - Cardiac Death and TVMI
 - Target Lesion Revascularization (TLR)
 - Major Adverse Cardiac Event (MACE)
Defined as death, myocardial infarction (Q wave and non-Q wave), emergent coronary bypass surgery, or clinically-driven repeat target lesion revascularization by percutaneous or surgical methods
 - Target Lesion Failure (TLF)
 - Target Vessel Failure (TVF)
 - Stent Thrombosis (ST)

Imaging Endpoint:

- The following secondary endpoint will be assessed at 6 months for subjects who received Myocardial Perfusion Imaging (MPI) per standard care at baseline:
 - Percentage of Myocardium with Reversible Ischemia per Myocardial Perfusion Imaging

Other clinical parameters of stress testing will be collected at baseline and at follow-up testing to assess change following the stenting procedure. These parameters include stress induced angina symptoms, incidence of ST-depression, and exercise capacity.

Angiographic Endpoints:

- The following Angiographic Endpoints will be assessed at 13 months post-procedure (for at least 20 patients):
 - Late Lumen Loss (LL)
 - Binary Angiographic Restenosis (BAR) rate (defined as >50% diameter stenosis (DS))
 - Percent Diameter Stenosis

3.3. Sample Size Justification

If the 12-month TLF rate of the Resolute Onyx 2.0 mm stent is shown to be significantly less than 19%, then the trial will be considered to have met its primary objective. In other words, the assessment of TLF is a testing with the following null and alternative hypotheses:

$$H_0: \pi \geq 19\% \text{ vs. } H_1: \pi < 19\%,$$

where π is the true Resolute Onyx 2.0 mm stent 12-month TLF rate.

The assessment of the null hypothesis will be carried out at the one-sided 0.05 level of significance. Rejection of the null hypothesis indicates the Resolute Onyx 2.0 mm stent 12-month TLF rate is significantly below 19%.

Accounting for a 10% clinical loss to follow-up and one-sided 0.05 level of significance, a sample size of 100 subjects yields more than 80% power to reject the above null hypothesis in favor of the alternative, assuming the true Resolute Onyx 2.0 mm stent 12-month TLF rate is 9.4%.

3.4. Analysis Strategy

Descriptive statistics will be presented for this study. Hypothesis testing with performance goal will be evaluated for primary endpoint.

4. Analysis Populations

Intent-to-Treat (ITT): For this trial, all subjects who sign the written informed consent and also have the study stent (Resolute Onyx 2.0 mm stent) introduced into the guide catheter will be counted in the ITT set, which will be the primary analysis set.

Per-Protocol (PP): The ITT population excluding subjects who do not meet certain key entry criteria (for exclusion criteria below, if any answer is “yes”, the subjects are excluded from PP population):

1. Did not receive any study device
2. Received study device, and another type of DES
3. Did not meet the following inclusion criteria:
 - a. General Inclusion 3: Subject has clinical evidence of ischemic heart disease, For single vessel disease: stable or unstable angina alone is sufficient. For multi-vessel treatment: a positive functional study or FFR to demonstrate functional need in 2.0 mm small vessel.
 - b. Angiographic Inclusion 1: The subject requires treatment of either:
 - i. A single target lesion amenable to treatment with a 2.0 mm stent
 - OR
 - ii. Two target lesions located in separate target vessels, with at least one of the target lesions amenable to treatment with a 2.0 mm study stent

- c. Angiographic inclusion 2: Target lesion(s) must be de novo lesion(s) in native coronary artery(ies)
4. Did not meet the following exclusion criteria:
- a. General exclusion 5: Evidence of an acute MI within 72 hours of the trial procedure:
 - a) Q wave myocardial infarction (QWMI)
 - OR
 - b) Elevated cardiac biomarker values [preferably cardiac troponin (cTn)] with at least one value above the upper reference limit (URL) and with at least one of the following:
 - Symptoms of ischemia
 - New or presumed new significant ST-segment–T wave (ST–T) changes or new left bundle branch block (LBBB)
 - Development of pathological Q waves in the ECG
 - Imaging evidence of new loss of viable myocardium or new regional wall

Note: Subjects with evidence or suspicion of an acute MI (per Investigator or Sub-Investigator determination) must have cardiac enzyme results reviewed prior to enrollment.
 - b. General exclusion 7: Planned PCI of any vessel within 30 days post-index procedure and/or planned PCI of the target vessel(s) within 12 months post-procedure. (no staged procedures)

Note: Refer to Table 1 Section 3.1.5 for additional procedure criteria for planned PCI of the target and other (non-target) vessel(s)
 - c. General Exclusion 8: During the index procedure, the target lesion(s) requires treatment with a device other than percutaneous transluminal coronary angiography (PTCA) prior to stent placement (including, but not limited to, cutting/scoring balloon, atherectomy, laser, thrombectomy, etc.)
 - d. General Exclusion 14: Currently participating in an investigational drug or another device trial that has not completed the primary endpoint or that clinically interferes with the current trial endpoints; or requires coronary angiography, IVUS or other coronary artery imaging procedures

Note: Trials requiring extended follow-up for products that were investigational, but have since become commercially available, are not considered investigational trials.
 - e. Angiographic Exclusion 2: Previous stenting in the target vessel(s):
 - a) within 9 months prior to procedure
 - b) ≤ 15 mm from the target lesion(s)

The primary endpoint will also be analyzed in PP population.

5. Interim Analysis

There is no planned interim analysis for this trial.

6. Statistical Methods of Analyses

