4.0 CLINICAL TRIAL DESIGN

The Medtronic RESOLUTE ONYX 2.0 mm Clinical Trial is a single arm, open label, multi-center trial enrolling at least 100 subjects with ischemic heart disease attributable to stenotic lesions of the native coronary arteries that are amenable to percutaneous treatment with a Resolute Onyx 2.0 mm stent. At least 20 subjects will be enrolled to receive an angiographic follow up at 13 months.

Subjects may receive treatment of one or two lesions, one lesion per target vessel, for a maximum of two target vessels. Only one lesion may be treated in a single target vessel. All treatment with the study stents is to be performed during a single index procedure. Refer to [Table 2](#) for additional stenting criteria.

In the event of one lesion to be treated with a 2.0 mm study stent and another lesion to be treated with a core size (2.25 mm - 4.0 mm) Resolute Integrity stent, the subject should be treated first with the core-sized stent. If the treatment of the first lesion fails or if the subject becomes unstable *before* a 2.0 mm study stent is attempted (stent introduced into guide catheter), the subject will not be enrolled, will not be followed, and will not be included in the primary analysis of this trial. Another subject should be enrolled to replace this subject for the primary analysis. If the treatment with the 2.0 mm study stent is attempted (stent introduced into guide catheter) but not implanted, the subject will be considered part of the Intention-to-Treat population (ITT) and will be followed through the 12 month endpoint and will be included in the primary analysis of this trial.

For subjects who have more than one lesion planned for treatment, a positive functional study or FFR should be performed in the vessel expected to receive the 2.0 mm study stent to demonstrate the functional need for treating such a lesion.

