5.4.4 Stenting Procedure

The aim is to maintain a homogeneous treatment strategy, and therefore all lesions should be treated with Resolute Integrity (2.25 mm - 4.0 mm) or Resolute Onyx (2.0 mm) stents. Potential interaction with other drug-eluting stents or coated stents has not been evaluated, and should be avoided.

RESOLUTE Onyx 2.0 mm Clinical Study
CONFIDENTIAL - May not be reproduced without written permission from Medtronic

A stent length should be selected so that the lesion can be covered with a single stent in order to avoid the use of multiple stents. Careful stent sizing is important to successful stenting. In general, the stent size should be chosen to match the diameter of the reference vessel and to correspond with the length of the lesion. The appropriate Resolute Onyx Stent size selected for the target lesion must be ≥ 3 mm longer than the lesion length in order to provide 1.5 mm of stent coverage on either side of the lesion.

The stent system will be prepared according to the Resolute Onyx Stent System IFU. The prepared delivery system will be advanced over the guide wire, through the guiding catheter to the target lesion site. The stent will be positioned across the lesion and placement will be confirmed by fluoroscopic angiographic test injections. Deployment of the stent should then be performed in accordance with the IFU.

Available Resolute Onyx 2.0 mm stent sizes are listed in [Table 5](#).

Table 5: Resolute Onyx 2.0 mm Stent Size Matrix

Nominal Expanded Inner Diameter (mm)	Stent Length (mm)						
	8	12	15	18	22	26	30
2.0	✓	✓	✓	✓	✓	✓	✓

Post-dilatation may be performed at the Investigator's discretion with appropriately sized (length and diameter) non-compliant balloon to assure that the stent is in full contact with the vessel wall. ***Do not use the stent delivery balloon for post-dilatation.***

For subjects with planned treatment of two lesions, ***the first lesion must be treated successfully and the subject must be clinically stable before treatment of the second lesion is attempted.***

Successful treatment of the first lesion is defined as:

- <10% residual diameter stenosis result is achieved (visual assessment)
- TIMI 3 flow is present post treatment
- No evidence of dissection (NHLBI Type C, D, E or F), thrombus or distal embolization at the first study lesion site post-treatment.

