Prior to attempted treatment of the second study lesion, subjects must be clinically stable without angina or ECG changes consistent with coronary ischemia. If the subject is not clinically stable, or shows signs or symptoms of possible coronary ischemia following treatment of the first study lesion, treatment of the second lesion should be deferred, if possible. Subsequent treatment of the second lesion should be with a study stent if performed during the trial index procedure. If the second lesion requires treatment after the index procedure, a non-study stent must be used.

For subjects with planned treatment of only one lesion but during the procedure a second lesion meeting trial criteria is identified, a Resolute Integrity (2.25 mm - 4.0 mm) or Resolute Onyx (2.0 mm) stent should be used if stenting is needed and treatment cannot be deferred. If the lesion does not meet trial criteria, a non-study stent should be used if stenting is needed and the lesion will be considered a non-target lesion for purposes of analysis.

RESOLUTE Onyx 2.0 mm Clinical Study**CONFIDENTIAL - May not be reproduced without written permission from Medtronic**

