5.4.5 Bailout

Bailout procedures should be avoided unless required for subject safety. If bailout procedures are performed, justification should be documented on the CRF.

If a subject in the trial experiences a major dissection or an occlusive complication (as evidenced by decreased target vessel flow, chest pain, or ischemic electrocardiogram (ECG) changes which do not respond to standard rescue techniques), bailout procedures may be performed. For these events occurring during the study procedure, additional stenting with Resolute Integrity (2.25 mm - 4.0 mm) or Resolute Onyx (2.0 mm) stents may be employed as a bailout treatment.

In this trial, the target lesion(s) is/are to be selected with the intent to cover each lesion with a single stent. If incomplete coverage occurs during the procedure, additional stenting with study stents may be employed to provide complete coverage.

It is recommended to overlap the Resolute Onyx stents 1-2 mm to avoid the potential for gap restenosis.

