A study deviation is defined as an event where the Investigator or site personnel did not conduct the trial according to the investigational plan, applicable laws or regulations, or the Investigator Agreement.

STUDY STENT

A study stent is defined as the Resolute Onyx 2.0 mm stent.

TARGET LESION

Any lesion treated or attempted to be treated during the study procedure. The target lesion is the treated segment starting 5 mm proximal to the stent and ending 5 mm distal to the stent.

TARGET LESION FAILURE (TLF)

Defined as cardiac death, target vessel myocardial infarction (Q wave and non-Q wave), or clinically-driven target lesion revascularization (TLR) by percutaneous or surgical methods

TARGET LESION REVASCULARIZATION (TLR)

Repeat PCI or CABG to the target lesion. See also clinically-driven target lesion revascularization.

TARGET VESSEL

The arterial segment and any branches and/or parent vessel that possess the target lesion. For this study, the target vessel can only be the left main (protected), LAD, Cx, RCA. Side branches less than 2.0 mm in diameter will not be considered 'significant' and therefore the disease in these vessels will not be considered significant.

RESOLUTE Onyx 2.0 mm Clinical Study**CONFIDENTIAL - May not be reproduced without written permission from Medtronic**

TARGET VESSEL FAILURE (TVF)

The composite endpoint comprised of cardiac death, target vessel myocardial infarction, or clinically-driven target vessel revascularization by percutaneous or surgical methods.

Target vessel failure will be reported when ANY of the following events occur:

- Recurrent MI occurs in territory not clearly attributed to a vessel other than the target vessel.
- Cardiac death not clearly due to a non-target vessel endpoint.
- Target vessel revascularization is determined.

TARGET VESSEL MYOCARDIAL INFARCTION (TVMI)

Target-vessel MI is defined as a MI that occurs in a territory that cannot be clearly attributed to a vessel other than the target vessel.

TARGET VESSEL REVASCULARIZATION (TVR)

Repeat PCI or CABG of the target vessel. See also clinically-driven target vessel revascularization.

THROMBOLYSIS IN MYOCARDIAL INFARCTION (TIMI) CLASSIFICATION¹⁵

TIMI 0	No perfusion.
TIMI 1	Penetration with minimal perfusion. Contrast fails to opacify the entire bed distal to the stenosis for the duration of the cine run.

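### Does the Per-Protocol rule on another type of DES remove subjects who were treated as the plan directs?

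*SAP*

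**What the plan says.** SAP Section 4 names ITT as the primary analysis set and adds that the primary endpoint will also be analysed in the PP set. PP is ITT less subjects who fail certain key entry criteria, and a yes to any listed item removes the subject. Three items matter here:

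- Rule 2: "Received study device, and another type of DES".
- Rule 3b.ii, which keeps subjects with two target lesions in separate vessels, "with at least one of the target lesions amenable to treatment with a 2.0 mm study stent".
- Rule 4, whose lead-in is "Did not meet the following exclusion criteria", followed by five exclusion criteria.

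Protocol 7.3 gives only the general PP definition and has no rule on other stents.

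On devices, Protocol Appendix 2 states: "A study stent is defined as the Resolute Onyx 2.0 mm stent". Protocol 4.0 provides for one lesion to receive the 2.0 mm stent and "another lesion to be treated with a core size (2.25 mm - 4.0 mm) Resolute Integrity stent". Protocol 5.4.5 allows that "additional stenting with Resolute Integrity (2.25 mm - 4.0 mm) or Resolute Onyx (2.0 mm) stents may be employed as a bailout treatment".

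**The concern.** Rule 2 defines neither type of DES nor a lesion or time limit. Since the study stent is Onyx 2.0 mm alone, Integrity can be read as another DES. Rule 2 would then remove subjects whose core-size lesion was treated as Protocol 4.0 and SAP 3.1 direct, or who received Integrity as a permitted bailout. Two programmers could build different PP sets from the same data and, in an open-label single-arm trial, the choice could be made with outcomes in view.

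With no time limit, a DES placed months later to treat a target lesion revascularization might also trigger the rule. That would remove a subject because of a primary-endpoint event and pull the PP rate down.

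Rule 4, taken literally, removes subjects who are free of the listed exclusions and keeps those who have them.

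**Working it through.** The plan gives no figure on this point, so the check is first one of text.

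**Does Integrity count as another type?**

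1. Rule 3b.ii sits in the same list and accepts two-lesion subjects with only one lesion suited to the 2.0 mm stent. SAP 3.1 directs Integrity for core-size lesions. If rule 2 caught Integrity, it would remove subjects whom 3b.ii expressly allows.
2. Protocol 5.4.4 asks for a homogeneous strategy using Integrity or Onyx, then adds: "Potential interaction with other drug-eluting stents or coated stents has not been evaluated, and should be avoided". The word other there sets further stents apart from both.
3. SAP 6.2 describes the companion stent as one of another size, while rule 2 speaks of another type.

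All three support the narrower reading, in which Integrity does not trigger rule 2.

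**Which procedure?** The stem limits the list to key entry criteria. Rule 1 concerns receipt of the study device, and the items under rules 3 and 4 are eligibility or index-procedure conditions. A stent placed at a later revascularization is not an entry criterion. In addition, the first footnote to SAP Table 1 directs the study device for acute or subacute closure within 30 days, so those early events would not trigger the rule if managed as written.

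**Rule 4.** Taken literally, it would remove nearly every eligible subject. The stem shows that the opposite is meant.

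**Size if the wider reading were used.** The documents do not give the share of subjects with Onyx plus Integrity.

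- From SAP 3.3: 100 subjects with 10% loss, so 90 evaluable; performance goal 19%.
- From SAP 6.2: exact binomial one-sided upper 95% limit.
- Assumed: 8 TLF events (8/90 = 8.9%, near the planned 9.4%) and a removed share of 10% to 30%.

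Upper limit = the 0.95 quantile of Beta(x + 1, n − x), for x events in n subjects.

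| Case | x/n | Upper limit |
|---|---|---|
| Narrower reading, none removed | 8/90 | 15.5% |
| Wider, 10% removed, 1 event among them | 7/81 | 15.6% |
| Wider, 20% removed, 2 events | 6/72 | 15.8% |
| Wider, 30% removed, 2 events | 6/63 | 17.9% |
| Wider, 20% removed, 1 event | 7/72 | 17.5% |
| Wider, 20% removed, no event | 8/72 | 19.2% |

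The last row needs none of the 8 events to fall among the 18 removed. If events are spread at random, the hypergeometric probability is C(72,8)/C(90,8) = 0.154.

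**Size if later revascularizations were removed.** Removing 1 to 4 event subjects gives 7/89 (upper limit 14.3%) to 4/86 (10.3%), against 15.5% for 8/90. The PP result would look better than it should, but all these limits, including 8/90, are below 19%.

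**The case for a change.** The strongest case for a change is that a pre-specified set should be programmable in only one way, and Section 4 neither states the narrower reading nor points to the sections that support it. The two sets differ as soon as one subject receives both stents, a combination the plan provides for. Settling the word type also leaves lesion and timing open. Protocol 5.4.4 says of a second lesion found during the procedure: "If the lesion does not meet trial criteria, a non-study stent should be used if stenting is needed". If that stent is a DES, rule 2 as written can remove a subject who was treated as the protocol directs.

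Part of this stands: the term is undefined, and whether a non-target lesion counts is not stated. But leaving such a subject out of PP is a defensible choice, because the protocol itself says that interaction with other DES has not been evaluated. Limiting the rule to target lesions would be a preference, not the correction of an error. The argument about removing outcome events is weaker, since it sets aside the entry-criteria stem that everyone relies on to read rule 4.

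**Conclusion.** No change is needed. Rule 2 leaves a detail open that an analyst would fill sensibly from the rest of the plan: Integrity is not another type, and the index procedure is meant. Rule 4 is a clerical slip whose intent is plain.

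The consequence is small under any reading. ITT decides the trial and keeps all these subjects, and PP has no success rule, so even a PP limit above 19% would not overturn the primary conclusion. The one crossing found (8/72, 19.2%) requires the less likely reading, an assumed 20% share with both stents, and no event among the 18 removed. The 8 events and the 10% to 30% shares are illustrations, not figures from the documents. If no subject receives Onyx with Integrity, the two readings of type give the same set.
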